TRIAL OBJECTIVES

Primary Objectives:

1. To determine if intraoperative margin assessment after excision of a cancer reduces reexcision procedures, compared to standard surgical practice by 9 months after primary surgery.2. To compare the total number of re-excision procedures required between groups and tissue weight resected after BCS, because of positive margins.

Secondary objectives:

- 1. To determine the effect of margin assessment on a) quality of life (QOL), b) cosmetic outcomes and cost-effectiveness (EQ5D).
- a) QOL in each group will be measured by using validated self-completion disease specific and generic instruments, FACT-B[11], HADS[12], health-related utility (EQ5D) and the body image scale of SABIS[13] administered at baseline (pre-surgery) and postal follow-up at 1,3,9 months post-surgery to permit calculation of Trial Outcome Index (FACT-B TOI). This assessment will permit area under the curve approach to analysis of differences between arms in QoL.[C1] Quality of life is a crucial variable if we are to understand the impact of MarginProbe, especially if the effect on re-excision rates is not of marginal significance. The effect of avoiding re-excision or mastectomy on the quality of life of women may act as a multiplier which makes the procedure worth (or alternatively not worth) undertaking even if the actual numbers of excisions and mastectomies avoided is marginal.
- b) Cosmetic evaluation, blind to randomisation assignment will be conducted at baseline and 9 months by observer using a symmetry based scale[14] and photographic measurements compared by observers blinded to randomisation. Two independent observers will use the symmetry-based ratings and undertake the photographic measurements to assess cosmetic outcomes. Inter-rater agreements will be calculated to check reliability of observations. Patient related outcomes will be measured using the Harvard Cosmesis Scale[21].

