Under the assumption that there is a halving in the re-excision rate (from 25% to 12.5%) including a halving in the mastectomy rate (from 10% to 5%), we estimate there will be an approximately 20% reduction in costs.

In addition to a cost-effectiveness analysis, we will estimate the budget and service impact of day case surgery to the NHS based on the experience of the trial and include the possibility of extending this treatment service to non-specialist centres.

The appropriate economic evaluation technique is a cost effectiveness analysis, in which any outcome benefits are compared to cost differences between the two strategies. To facilitate this, a comprehensive comparison of the costs of the two groups will be undertaken. For each patient group, the following resource data will be collected using hospital records for in-patient resource use and patient-held diary cards for care in the immediate discharge period:

1. Length of pre- and post-operative hospital stay (in days/nights).

- 2. Number of outpatient clinic visits (planned and unplanned).
- 3. Use of capital equipment and supplies (e.g. probes).
- 4. Number of consultations with GP (at home or in surgery).
- 5. Number of contacts with District Nurses and/or breast specialist Nurses.

6. Resources used in therapy (e.g. surgery, MarginProbe, Radiation treatment: WBRT; IORT; none)

7. Patient carer trips associated with hospital care (mode of transport and cost).

8. Other costs associated with treatment (e.g. meals, loss of earnings, etc.).

Quality of Life assessments: QoL will be measured in each group by using validated selfcompletion disease specific and generic instruments, FACT-B[11], HADS[12] and EQ5D for healthrelated utility, together with the body image scale of SABIS[16]. These will be administered at baseline (pre-surgery) and by postal follow-up at 1,3,9 months post-surgery, permitting calculation of Trial Outcome Index (FACT-B TOI).

If women are scheduled for chemotherapy before re-excision procedures, the final assessment at 9 months will ensure all have completed therapeutic surgery. A window of +3 months for the collection of details regarding re-excision procedures is provided.

Data Flow Diagram:

CRFs, Questionnaires and Patient Diaries completed at site/ returned to site teams

CRFs returned to CTU

CTU perform data entry and track the CRF pages

CTU raise data queries for sites

Sites return data queries to CTU

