Loss to follow up that will influence the collection of valid data for the co-primary endpoints is not expected in this study. The co-primary endpoint data is obtained during the (initial) surgery and during a period of up to two weeks following it. Additionally, this data is collected routinely as part of the subject's standard treatment. In the pivotal study there was no loss to follow-up.

Loss to follow up that will influence the collection of patient questionnaires and diaries at 1, 6 and 9 months following the end of surgical treatment, will be minimized by letters and reminder phone calls to the patients, and also by providing patients with stamped addressed envelopes.

Sites will also be provided a 3 month window in order to collect data and complete photographs for the 9 month period; these can be completed up to 12 months post-surgery.

3. Trials Procedures

Baseline/screening visit:

- Eligibility criteria
- Informed consent
- Demographics Baseline characteristics(height, weight, bra cup and band size)

- Relevant medical history
- Pre-operative information
- Disease characteristics
- FACT B +4, HADS, EQ5D and SABIS Questionnaires administered

Operative visit:

- Procedural characteristics
 - Surgery information
 - o Device use information, including failures and malfunctions
 - \circ $\;$ Lumpectomy cavity shavings performed based on visual inspection and palpation $\;$
 - Lumpectomy cavity shavings performed based on device use (Device arm only)
- Intraoperative imaging use
 - Performed (Y/N)
 - o Imaging technique
 - Imaging result (when applicable)
 - o Lumpectomy cavity shavings performed based on intraoperative imaging assessment
- Pathology
 - Tumour type
 - o Margin status main ex-vivo lumpectomy specimen and lumpectomy cavity shavings
 - o Margin depth
 - Specimen dimensions
- Adverse events and Serious Adverse Events

Follow up visits (month 1, 3 and 9):

• FACT B +4, HADS and EQ5D Questionnaires and Patient Diary Cards Administered

MarginProbe Device

In patients randomised to the device arm, the MarginProbe will be used after radiological examination of the operative specimen and ensuring that the margins are radiologically clear. The MarginProbe will then be used to examine all six outer surfaces of the lumpectomy specimens with five to eight measurements per face..

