Quality of Life assessments: QoL will be measured in each group by using validated selfcompletion disease specific and generic instruments, FACT-B[11],HADS[12] and EQ5D for healthrelated utility, together with the body image scale of SABIS[16]. These will be administered at baseline (pre-surgery) and by postal follow-up at 1,3,9 months post-surgery, permitting calculation of Trial Outcome Index (FACT-B TOI).). Analyses of covariance will be used to compare QOL scores between the groups at 6 months follow-up, adjusting for baseline scores and other potential confounding factors (e.g. Centre, chemotherapy use). In addition, longitudinal regression analysis, using generalised estimating equations, will be used to compare the QOL scores between groups over the whole follow-up period (1, 3 and 9 months post randomisation).

Missing data: Missing QOL data at follow-up time points will be adjusted for in the statistical analysis using multiple imputation procedures.

Statistical Approach: All analyses will be by intention-to-treat using the conventional twosided 5% significance level. The statistical software packages SPSS and STATA will be employed to carry out the statistical analyses.

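### The quality-of-life ANCOVA is set at 6 months, but the assessment schedule collects follow-up questionnaires only at 1, 3 and 9 months

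*Protocol*

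**What the plan says.** The quality-of-life paragraph in Section 4 (Data Analysis and Statistical Considerations) has three consecutive statements on timing:

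- Questionnaires are completed before surgery and then "by postal follow-up at 1,3,9 months post-surgery, permitting calculation of Trial Outcome Index".
- "Analyses of covariance will be used to compare QOL scores between the groups at 6 months follow-up", with adjustment for baseline score and for other potential confounders, for which the examples are "e.g. Centre, chemotherapy use".
- Generalised estimating equations (GEE) compare the arms over the whole follow-up, given as 1, 3 and 9 months after randomisation.

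Elsewhere in the Protocol:

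- Trial Objectives, secondary objective 1a: "administered at baseline (pre-surgery) and postal follow-up at 1,3,9 months post-surgery to permit calculation of Trial Outcome Index". It adds that this supports an area-under-the-curve comparison of the arms.
- Section 3, Quality of Life assessments: "administered at baseline (pre-surgery) and by postal follow-up at 1,3,9 months post-surgery, permitting calculation of Trial Outcome Index".
- Trials Procedures: "Follow up visits (month 1, 3 and 9", listing FACT-B, HADS, EQ5D and diary cards.
- Schedule of Assessments: questionnaire entries at baseline, 1, 3 and 9 months, with no 6-month column.
- Section 3, Minimizing loss to follow up: "collection of patient questionnaires and diaries at 1, 6 and 9 months following the end of surgical treatment".

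Section 4 also says that quality-of-life data missing at follow-up time points will be handled by multiple imputation.

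**The concern.** A planned comparison names a visit that the schedule does not contain. Quality of life is a secondary objective, but Trial Objectives calls it crucial and says it could settle whether the device is worth using if the surgical benefit turns out marginal. The ANCOVA is the only quality-of-life comparison tied to one time point. Unless the time point is corrected in advance, either 3 or 9 months could be put in its place, and in a trial where patients know their allocation that choice should not be left open.

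The same model names chemotherapy use as a possible confounder. If chemotherapy always starts after randomisation, it cannot confound a randomised comparison. Adjusting for it could instead distort the estimated effect of allocation.

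**Working it through.** **Step 1: set the stated times side by side.**

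| Place in the Protocol | Months | Counted from |
|---|---|---|
| Trial Objectives, 1a | 1, 3, 9 | surgery |
| Section 3, Quality of Life assessments | 1, 3, 9 | surgery |
| Trials Procedures, follow-up visits | 1, 3, 9 | not stated |
| Schedule of Assessments | 1, 3, 9 | surgery |
| Section 4, sentence before the ANCOVA | 1, 3, 9 | surgery |
| Section 4, ANCOVA | 6 | not stated |
| Section 4, sentence after the ANCOVA (GEE) | 1, 3, 9 | randomisation |
| Section 3, Minimizing loss to follow up | 1, 6, 9 | end of surgical treatment |

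Six statements, including the schedule itself, agree on 1, 3 and 9. One sentence supports a 6-month questionnaire. It drops month 3 and uses a different clock.

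**Step 2: can any collected questionnaire count as a 6-month score?** The only window given is forward: the 9-month data may be collected up to 12 months. No window brings the 3-month or 9-month form to 6 months. The section on follow-up and data collection mentions an evaluation about 6 months after the end of surgical treatment, but that concerns cosmetic status, not questionnaires. Under the schedule, therefore, 0 of 460 patients have a 6-month score.

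**Step 3: can imputation fill the gap?** Multiple imputation needs some patients with the outcome observed, so that its relation to the other visits can be estimated. With no 6-month scores at all, any imputed value would come from assumption alone. The Protocol's own rule also covers only data missing at follow-up time points, and the schedule does not make 6 months one of them.

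**Step 4: does the time origin matter?** Surgery and randomisation fall on the same day, because patients are randomised in theatre, so those two origins coincide. The end of surgical treatment does not. The Background puts re-excision 5 to 6 weeks after the first operation, and the design rates are 25% re-excised in the control arm and 12.5% in the device arm. On that clock the follow-up date shifts for more control patients than device patients. The origin therefore has to be reconciled along with the months.

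**Step 5: are the TOI power figures affected?** Inputs from the sample size section: SD 15, two-sided 5%, 230 per group, differences 4.5 and 3.9. Power is approximately Φ(difference / (SD × √(2/n)) − 1.96).

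- Standard error: 15 × √(2/230) = 1.399.
- Difference 4.5: 4.5/1.399 − 1.96 = 1.257, power 89.6% (stated 90%).
- Difference 3.9: 3.9/1.399 − 1.96 = 0.828, power 79.6% (stated 80%).

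The exact noncentral t calculation gives 89.4% and 79.5%. The stated figures reproduce and do not depend on which collected visit is used.

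**Step 6: when does chemotherapy occur?** Randomisation takes place in theatre after excision (Section 3, Randomisation procedure). Neoadjuvant systemic therapy is an exclusion criterion. Section 3 envisages chemotherapy between the first operation and a re-excision. Chemotherapy use is therefore a post-randomisation variable by design. By contrast, the primary-endpoint and tissue-weight models in Section 4 name only Centre and DCIS versus invasive disease as example covariates.

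**The case against.** Several points on the other side stand.

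- A reader might infer that quality of life is left without any comparison between arms. It is not. The GEE analysis and the area-under-the-curve approach both use collected time points and need no choice of visit.
- A reader might say flatly that the outcome is entirely missing. That holds only once the contradiction is settled in favour of the schedule. The Protocol does contain one sentence with 6-month questionnaires, so the exact finding is an internal contradiction. That sentence still does not rescue the ANCOVA, because it conflicts with the visit list and the schedule.
- A choice of time point after results are known is a risk, not an established fact. The SAP is not shown and may fix the visit. Even so, it would have to depart from the Protocol to do so.
- The TOI power statement might look faulty because it names no visit. It reproduces, and a two-sample calculation with a given SD needs no visit label.
- On chemotherapy, the covariate is only an example. The Protocol does not say that chemotherapy is decided on final pathology, and it says that management after the procedure is identical in both arms. Bias would require allocation to affect chemotherapy use. That is possible, since allocation changes what tissue is removed and whether re-excision follows, but it is not shown.

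**Conclusion.** The point holds as an internal contradiction that makes one stated analysis impossible to run under the Protocol's own schedule. Its reach is one of three quality-of-life comparisons, on a secondary objective. The primary endpoint, the sample size and the TOI power figures are untouched. This rests on taking the Schedule of Assessments, and the five other statements that agree with it, as the intended collection plan.

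The documents do not support the stronger readings that quality of life cannot be analysed, that the power statement is wrong, or that the chemotherapy adjustment produces a known bias. Chemotherapy use is wrongly described as a confounder in a randomised comparison, but this is a secondary point and its size cannot be derived from the Protocol. Overall: should be fixed.

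**What to change.** Before any outcome data are seen:

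1. In Section 4, set the ANCOVA at a collected time point. Nine months is the natural choice: it is the last scheduled assessment, and Section 3 says therapeutic surgery will be complete for all patients by then.
2. In Minimizing loss to follow up, reconcile the sentence with the schedule in both months and time origin, and use one origin throughout (surgery, randomisation or end of surgical treatment).
3. In the main quality-of-life model, adjust for baseline score and pre-randomisation factors: Centre and DCIS versus invasive disease as known before randomisation. Keep any chemotherapy-adjusted model as a sensitivity analysis.

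The cost is wording in the Protocol, carried into the SAP. No new data, visits or patients are needed.

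### Quality of life is given weight in judging the device, but no method or time point is designated for FACT-B TOI, the one powered score, and the single-visit analysis falls at an unscheduled 6 months

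*Protocol*

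**What the plan says.** Under Trial Objectives, secondary objective 1a, the protocol gives quality of life a part in the overall judgement: "The effect of avoiding re-excision or mastectomy on the quality of life of women may act as a multiplier which makes the procedure worth". The sentence allows for the opposite verdict as well, and it is meant to cover the case where the surgical gain is small: "even if the actual numbers of excisions and mastectomies avoided is marginal". The same paragraph says of the questionnaires at baseline, 1, 3 and 9 months: "This assessment will permit area under the curve approach to analysis of differences between arms in QoL".

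The analysis is in section 4, Quality of Life assessments. The instruments are FACT-B (giving the TOI), HADS, EQ5D and the SABIS body image scale. The first method is at a single visit: "Analyses of covariance will be used to compare QOL scores between the groups at 6 months follow-up", with adjustment for baseline and other factors. The second follows directly: "In addition, longitudinal regression analysis, using generalised estimating equations, will be used to compare the QOL scores between groups over the whole follow-up period", given there as 1, 3 and 9 months. Statistical Approach then sets one rule for everything: "All analyses will be by intention-to-treat using the conventional twosided 5% significance level".

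The sample-size text (sections 3 and 4) states 90% power for a TOI difference of 4.5 and 80% for 3.9, with SD 15 and a two-sample t-test. No other quality-of-life score has a power statement.

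The Schedule of Assessments places the questionnaires at baseline, 1, 3 and 9 months. Only the paragraph on minimising loss to follow-up lists 1, 6 and 9 months.

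**The concern.** A secondary outcome that is described and not used to decide anything can be analysed in several ways without much harm. Here the protocol says in advance that quality of life may tip the judgement on the device. An outcome with that weight needs one stated comparison behind it. The protocol points to a score by powering TOI alone, but does not say which analysis of TOI, at which time, is the one that counts. It also leaves three other instruments at the same 5% level.

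The 6-month ANCOVA makes this worse. It cannot be run on the questionnaires in the schedule, so someone must move it to 3 or 9 months. If that is done after data are seen, it is one more free choice.

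At stake is a conclusion that the device helps (or harms) quality of life, drawn from whichever of several overlapping tests reached p<0.05. The women know their allocation and complete the questionnaires themselves, and the Blinding and bias paragraph itself anticipates expectation and disappointment effects. Naming one contrast does not remove reporting bias, because the bias would shift that contrast too. It does stop selection among tests from being added to it.

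**Working it through.** **1. The plan's own figure.** Inputs from the sample-size text: SD 15, 230 per group, two-sided 5%. Standard error of the TOI difference = 15 × √(2/230) = 1.399.
- Difference 4.5: 4.5/1.399 = 3.217; 3.217 − 1.960 = 1.257; power 89.6% (stated 90%).
- Difference 3.9: 3.9/1.399 = 2.788; 2.788 − 1.960 = 0.828; power 79.6% (stated 80%).

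The statement is reproduced for 230 analysed per arm. It describes one test of one score.

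**2. Upper reference, independent tests.** Four scores by two methods is 8 tests: 1 − 0.95⁸ = 33.7%, and in the favourable direction 1 − 0.975⁸ = 18.3%. Adding AUC makes 12 tests: 1 − 0.95¹² = 46.0%, favourable 1 − 0.975¹² = 26.2%. These overstate the risk because the methods reuse the same data.

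**3. Allowing for correlation.** The protocol gives no correlations, so these are assumptions: 0.3 to 0.7 between scores and r = 0.5 to 0.7 between any two visits. The 9-month visit stands in for the uncollected 6 months. With Z₀, Z₁, Z₃, Z₉ the standardised arm differences at each time under no effect:
- ANCOVA: Z₉ − rZ₀
- Longitudinal (GEE) contrast: (Z₁ + Z₃ + Z₉)/3 − rZ₀
- AUC by trapezoids over 0, 1, 3, 9 months: 0.5Z₀ + 1.5Z₁ + 4Z₃ + 3Z₉, either unadjusted or with the baseline term replaced by −8.5rZ₀

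Each is scaled to unit variance. The correlation between ANCOVA and GEE is √[(1 + 3r)/(3(1 + r))]. For r = 0.5 this is √(2.5/4.5) = 0.75; for r = 0.7 it is √(3.1/5.1) = 0.78. The methods overlap but are far from interchangeable.

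Simulated chance of at least one |z| > 1.96, four scores (400,000 replicates per setting, ranges over r):

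| Correlation between scores | One method | ANCOVA + GEE | of which favouring device | plus AUC, adjusted | plus AUC, unadjusted |
|---|---|---|---|---|---|
| 0.3 | 17% | 26–27% | 13–14% | 28–29% | 35–36% |
| 0.5 | 16% | 24% | 12% | 26% | 32–33% |
| 0.7 | 13% | 20% | 10% | 22% | 27–28% |

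Over the whole grid, including single values before rounding, two methods give about 20% to 27%, and three give about 21% to 36%. For TOI alone the chance is about 8% with two methods, about 9% with adjusted AUC added and about 11% with unadjusted AUC. If HADS is counted as two scores (a further assumption), two methods give about 22% to 32%.

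**4. After the fix.** One TOI contrast at two-sided 5% has a 5% error rate by construction and keeps the planned power of about 90% and 80%. Splitting 5% over four instruments (0.0125 each, critical value 2.498) would reduce it: 3.217 − 2.498 = 0.719, power 76.4%; 2.788 − 2.498 = 0.290, power 61.4%.

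**The case against.** Several points on the other side have force.

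- **This belongs in the statistical analysis plan.** Ranking secondary scores and controlling multiplicity are commonly left to that document, which was not available. Mere silence would not be a finding. But the protocol is not silent: it states the decision weight, names the methods, fixes 5% for all analyses and sets a visit that its schedule lacks. Those statements must be reconciled here.
- **The multiplier sentence is about valuing operations avoided.** This is a fair reading. A reader might infer that quality of life is a second route to success that could rescue a failed primary comparison. The protocol does not say so: marginal there describes the number of operations avoided, not a failed test. What stands is the narrower point that quality of life is given weight in the conclusion.
- **Only two methods are planned.** Section 4 has ANCOVA and GEE. The objectives say only that AUC will be possible, and the t-test is a planning device. This stands, so the two-method figures lead.
- **TOI is already singled out.** This also stands. A reader might infer that the plan has no key score at all; the power statement contradicts that. The missing part is the method and time point.
- **Six months does appear elsewhere.** The loss-to-follow-up paragraph lists it, but that conflicts with the Schedule of Assessments, the objectives and section 4's own list of visits.

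Requiring a significant primary result before testing quality of life is also open to objection. It would block a formal test of harm exactly when the device fails, although the protocol wants quality of life to be able to count against the device. It is not recommended here.

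**Conclusion.** The point holds in a limited form. The protocol gives quality of life weight in judging the device and powers one score. It designates no method or time for that score, plans overlapping analyses of four instruments at an unadjusted 5%, and puts one of them at a visit its schedule does not contain.

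Under the assumed correlations, a chance p<0.05 somewhere arises in about 20% to 27% of trials with the two planned methods, and a chance result favouring the device in about 10% to 14%, against 5% and 2.5% for a single test. For TOI alone the inflation is modest, to about 8%. The exact figures depend on the assumed correlations and shrink as the scores become more alike, but every setting examined exceeds 5%.

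A reader might infer that a spurious quality-of-life success is likely. The numbers do not support that: even 12 independent tests give 46.0% in either direction and 26.2% in the device's favour. The risk is materially inflated, no more than that. The change is worth making before database lock; it does not call the primary comparison into question.

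**What to change.** In section 4, Quality of Life assessments, name one key contrast: the between-arm difference in FACT-B TOI from the baseline-adjusted longitudinal model, averaged over 1, 3 and 9 months, tested at two-sided 5%. State that the other scores, the single-visit ANCOVAs and any AUC analysis are supportive, reported as estimates with 95% confidence intervals.

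Replace the 6-month ANCOVA time with a collected visit, and bring the loss-to-follow-up paragraph into line with the Schedule of Assessments.

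In secondary objective 1a, word the multiplier sentence so that any weight given to quality of life in the conclusion, for or against the device, rests on the named contrast.

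The cost is wording only, with no extra patients or data and no loss of the planned TOI power. The downside is that HADS, EQ5D, SABIS and the alternative TOI analyses can no longer support a claim on their own.
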